6.4. Handling of Dropouts or Missing Data

There will be no imputation for missing data unless specified otherwise.

General rule for the imputation of dates

If the adverse event (AE) onset date is missing or partial, the date will be compared as far as possible with the date of first dose of study medication when determining whether or not the AE is present at baseline. In this case, the AE will be assumed to be treatment emergent, unless there is clear evidence (through comparison of partial dates) to suggest that the AE started prior to the first dose of study medication.

Efficacy analysis

The chosen method of analysis for the longitudinal data, MMRM, can handle missing data, as it uses all available data across subjects to estimate parameters. Under the assumption of data being MAR or the non-random missing data is ignorable, the estimates based on restricted maximum likelihood (REML) are unbiased. In the Bayesian analysis, under the assumption of MAR and distinct parameters determining the probability model and missingness mechanism, Bayesian inferences can be obtained for model parameters using a likelihood based only on the observed data (Gelman et al. 2004).

Repeated measures analyses will only use data from visits at which the data were scheduled to be collected (Andersen and Millen 2013). When subjects discontinue from the study early, there may be efficacy or safety data measurements at visits at which the variables were not scheduled to be collected. These data will be used in all other analyses.

Subjects with missing baseline data or with no postbaseline visit data will not be included. The only exception to this is for the primary analysis (see Section 6.5).

6.5. Handling Missing Items for Scales

Total and subscale scores for questionnaire-based safety and efficacy outcome measures will be derived from individual items. If any of the individual items are missing or unknown, every effort will be made to obtain the score for the missing item or items. If this is not possible, any total or sum involving that item will be considered missing. However, imputations will be adopted for the Alzheimer's Disease Assessment Scale – Cognitive subscale (ADAS-Cog) if complete data cannot be gathered and potentially for the baseline measurements of the primary outcome, CoA. For additional considerations due to the COVID-19 pandemic, see Section 6.12.7.

ADAS-Cog₁₃

For the 13-item Alzheimer's Disease Assessment Scale – Cognitive subscale (ADAS-Cog₁₃), if 4 or fewer of a total of 13 items (approximately 30%) are missing, the total score (maximum = 85) will be imputed as follows: The total from the remaining items will be multiplied by a factor that includes the maximum score for the missing items. For example, if the first item, "Word-Recall Task," which ranges from a score of 0 through 10 (maximum = 10), is missing, and the second item "Commands," which ranges from a score of 0 through 5 (maximum = 5), is missing then the multiplication factor = $85 / (85 - [10 + 5]) = 85 / 70 = 1.21$. Thus, the total score for this example will be the sum of the remaining 11 items multiplied by 1.21. The imputed number will be rounded up to the nearest integer. If more than 4 items are missing, the total score for ADAS-Cog₁₃ at that visit will be considered missing. The same imputation technique will be applied to the 11-item Alzheimer's Disease Assessment Scale – Cognitive subscale (ADAS-Cog₁₁) subscore.

CoA

Missing baseline data for CoA will be imputed using a regression approach. A simple linear regression model of CoA at baseline in terms of CoA scores at screening will be produced. Scores from the 2 screening assessments will be included as separate explanatory variables (first screening score and second screening score). This model will be based on data from subjects who have both screening and baseline CoA scores.

If missing, a subject's Visit 2 baseline score will be imputed with a predicted value from the model based on the subject's own CoA screening data. If a subject is missing both baseline and screening visit CoA data, the subject will be excluded from the analyses of CoA.

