3.2. Background

Lewy Body Dementia (LBD), including Parkinson’s disease dementia (PDD) and DLB, is a progressive neurodegenerative disorder associated with alpha-synuclein deposition, Lewy body pathology, and degeneration of nigro-striatal dopaminergic neurons. According to the Parkinson’s Disease Foundation, Parkinson’s disease (PD) affects approximately 1 million people in the United States (U.S.) and 7 to 10 million people worldwide (Statistics on Parkinson’s). It is estimated that up to 78% of patients with PD will develop dementia (PDD) in their lifetime (Aarsland et al. 2005). DLB is the second most common dementia after Alzheimer’s disease (AD) and affects 1.4 million individuals in the U.S., representing an estimated 15-20% of all dementia cases worldwide (Lewy Body Dementia Association [<https://www.lbda.org/go/10-things-you-should-know-about-lbd>]).

LBD is pathologically characterized by intraneuronal inclusions of Lewy bodies throughout subcortical and cortical brain regions, a major component of which is misfolded aggregated α -synuclein (Beyer et al. 2009). Lewy body formation and propagation is accompanied by progressive neurodegenerative processes, particularly affecting the dopaminergic and cholinergic neurons (Harding and Halliday 2001; Klein et al. 2010; Colloby et al. 2012). These neuropathological findings are largely indistinguishable between DLB and PDD and have thus led the field to consider them the same disease.

The cognitive impairments of PDD and DLB also overlap. Progressive executive dysfunction and visual-spatial abnormalities are noted in both, but memory remains relatively intact early in the course of disease (Lippa et al. 2007). Prodromal and non-motor features are similar for both conditions and include REM sleep behavior disorder, hyposmia, prominent visual hallucinations, fluctuations in arousal, autonomic dysfunction, and depression/anxiety. They share neuroimaging characteristics with overlapping patterns of atrophy, glucose utilization, and neurotransmitter changes (cortical cholinergic deficits [Colloby et al. 2016] and striatal/cortical

dopaminergic deficits [Klein et al. 2010]). Although once considered as two separate entities, the constellation of supportive pathological, clinical, imaging, and neurochemical data suggest PDD and DLB fall within a spectrum of the same disease (Berg et al. 2014; Gomperts 2016; Friedman 2018; Jellinger 2018; Jellinger and Korczyn 2018).

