The ADAS-Cog₁₃ measures severity of impairment. Higher scores reflect greater cognitive impairment. The maximum score is 85. Most item scores are based on the number of words not recalled or the number of errors: Word Recall, Commands, Constructional Praxis, Delayed Word Recall, Naming, Ideational Praxis, Orientation, and Word Recognition. Remembering Test Instructions is rated based on the number of reminders during the Word Recognition task. Spoken Language Ability, Comprehension of Spoken Language, and Word-finding Difficulty are rated on a scale of severity of dysfunction ranging from 0 to 5, where 0 = no impairment, 1 = very mild, 2 = mild, 3 = moderate, 4 = moderately severe, and 5 = severe. The score for the Number Cancellation item ranges from 0 to 5, based on ranges of numbers of target items correctly crossed off by the subject within the time limit; the fewer correct responses, the higher the score.

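### ADAS-Cog13 proration in SAP 6.5 assumes equal proportional loss across items, always rounds toward impairment, and limits missing data by item count rather than points

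*SAP*

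**What the plan says.** SAP 6.5 makes ADAS-Cog an exception to its default that a scale total with a missing item is itself missing. An ADAS-Cog13 total is imputed "if 4 or fewer of a total of 13 items (approximately 30%) are missing". The rule reads: "The total from the remaining items will be multiplied by a factor that includes the maximum score for the missing items". The worked example takes Word Recall (10 points) and Commands (5 points) as missing and arrives at 85/70, printed as 1.21. Then: "The imputed number will be rounded up to the nearest integer". With more than four items missing, the total is missing. The same technique is applied to ADAS-Cog11, for which no maximum or item limit is given.

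ADAS-Cog13 is a secondary endpoint analysed by a frequentist MMRM (SAP 6.12.3). SAP 6.12.5 plans a sensitivity analysis for imputed CoA baselines, but nothing comparable for imputed ADAS-Cog totals.

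**The concern.** Three features of the rule look wrong.

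- **Scaling.** Proration by points assumes that a subject is proportionally as impaired on the missing items as on the observed ones. The scale mixes memory, language, praxis and attention (Protocol 9.1.2.1.3), and Protocol 3.2 describes an uneven picture: "Progressive executive dysfunction and visual-spatial abnormalities are noted in both, but memory remains relatively intact early in the course of disease".
- **Rounding.** Higher scores mean greater impairment, so rounding up is a one-sided error toward impairment. No reason is given for it.
- **Limit.** The cut-off counts items, although items carry different numbers of points.

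At stake is the accuracy of individual ADAS-Cog13 totals, hence the precision of a secondary contrast and, under further conditions, its bias.

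**Working it through.** **Inputs.** Protocol 9.1.2.1.3 gives the scale maximum: "The maximum score is 85". It gives three language items "rated on a scale of severity of dysfunction ranging from 0 to 5", and it states: "The score for the Number Cancellation item ranges from 0 to 5". SAP 6.5 gives Word Recall 10 and Commands 5. Neither document prints maxima for the other seven items, any item means, or an expected frequency of missing items.

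**1. The SAP's own factor.** 85/(85 − 15) = 85/70 = 1.2143, which reproduces the printed 1.21.

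**2. Scaling error.** Let M be the maximum points on the missing items, and let p_obs and p_miss be the fractions of available points lost on observed and missing items.

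- Imputed total before rounding: p_obs(85 − M) × 85/(85 − M) = 85 p_obs
- True total: p_obs(85 − M) + p_miss M
- Error: M × (p_obs − p_miss) = M × g

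The gap g is not in the documents, so a range is assumed:

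| Missing items | M | g = ±0.2 | g = ±0.4 | g = ±0.6 |
|---|---|---|---|---|
| One 5-point item | 5 | ±1 | ±2 | ±3 |
| SAP example | 15 | ±3 | ±6 | ±9 |
| Word Recall plus three 5-point items | 25 | ±5 | ±10 | ±15 |

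At g = 0 the scaling error is zero.

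**3. The same in scores.** Take M = 15 and a true total of 30.

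- Missing items truly sum to 2: 28 × 85/70 = 34, error +4.
- They sum to 5: 25 × 85/70 = 30.36, recorded as 31, error +1.
- They sum to 10: 20 × 85/70 = 24.29, recorded as 25, error −5.

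**4. Rounding.** 85/70 = 17/14, so an integer observed sum gives a whole number only when it is a multiple of 14. The other 13 of every 14 sums are pushed up. Over the 71 possible sums 0 to 70 the excess runs from 0 to 13/14 = 0.93, with mean 0.46. Ordinary rounding to nearest would average +0.04; no rounding gives 0. Using the printed 1.21 in place of 85/70 changes the rounded-up total by 1 point for 8 of the 71 sums. For example, 19 × 85/70 = 23.07 becomes 24, whereas 19 × 1.21 = 22.99 becomes 23.

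**5. The limit.** By items, 4/13 = 30.8%. By points, the six items with printed maxima total 10 + 5 + (3 × 5) + 5 = 35, so the other seven share 85 − 35 = 50. With integer maxima, the three largest of those seven total at least 22, because 3 × 50/7 = 21.4. Word Recall plus those three is therefore at least 10 + 22 = 32 points, and 32/85 = 38%. Four 5-point items are 20/85 = 24%.

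**The case against.** The strongest reply is that this is ordinary prespecified proration with a worked example and a cap, applied to one of several secondary outcomes in a study that calls itself exploratory. SAP 6.5 and Protocol 10.3.1.1 require sites to try to recover missing items first. Protocol 9.1.2 has raters take respondents through each measure orally to limit gaps. SAP 6.12.7 repeats the relevant scales without virtual-visit data. All of that stands, and it reduces the number of affected records. It does not change the error in a record that is imputed, and the virtual-visit analysis leaves imputed in-clinic totals in place.

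Several stronger readings are tempting and should not be made.

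- A reader might infer that items are known to differ greatly in difficulty, so that errors are large. The sentence in Protocol 3.2 is qualitative and concerns early disease, while the trial enrols MoCA 10 to 23. It is a reason to doubt equal proportional loss, but it cannot give its size.
- A reader might infer that four items can reach 40 of 85 points (47%). That needs maxima for three items that neither document prints.
- A reader might infer that totals are usually complete at baseline and imputed later, so that the error passes whole into the change score. The documents do not say so, and errors partly cancel if the same items are missing at both visits.
- A reader might infer that drug effects make item missingness differ by arm. No passage supports this.

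**Conclusion.** The point holds in limited form. The scaling error per imputed total is exactly M × g. It can reach several points in either direction, but the gap sizes used here are assumptions and the frequency of imputation is unknown. With a single missing 5-point item the error is 2 points or less unless the gap exceeds 0.4. The rounding error needs no assumption about item profile: it is upward only and under 1 point. That the limit misses its stated 30% in points follows from the documents' own maxima, assuming only that the unlisted maxima are whole numbers.

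For the treatment contrast the main effect is added noise. Bias requires item missingness or item profile to differ between arms, and the documents do not establish either. The point is minor but cheap to correct.

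**What to change.** In SAP 6.5:

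- Use the exact factor 85/(85 − M), and do not round the imputed total up.
- Set the limit by points: impute only if no more than 25 of 85 points are missing (25/85 = 29%, in line with the stated 30%). Beyond that the total is missing and the MMRM handles it under the missing-at-random assumption in SAP 6.4.
- Apply the same rule to ADAS-Cog11, with its own maximum stated and the limit set at the same share of points.

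In SAP 6.12.5, add a sensitivity analysis that treats every imputed ADAS-Cog total as missing, parallel to the one already planned for imputed CoA baselines, and report the number of imputed totals by arm. This is needed because the points limit does not remove the scaling error: at M = 25 it is still ±5 at a gap of 0.2.

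The cost is SAP wording, minor programming and a few more missing totals; no new data are needed. SAP Version 3 was approved after unblinding, so the change should be justified as such in the study report.

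Item-level regression is optional. ADAS-Cog13 is scheduled only at Visits 2, 8, 11 and early termination, so a missing baseline item has no earlier score to regress on. The CoA regression in SAP 6.5 uses composite scores, not items, and so is not a ready template.

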6.6. Multicenter Studies

Approximately 75 sites, predominantly in the United States (with some sites in Canada), will be participating in the trial. In the IWRS process, minimization will be adopted to maintain balance in treatment allocation at each site. Site is not an intended covariate for any statistical modeling, as the majority of sites are expected to only recruit a small number of subjects. Adjusting for such a large number of small sites would result in a high possibility of detecting a false site effect, due to multiplicity, and could also result in unreliable estimates of the treatment effect.

6.7. Multiple Comparisons/Multiplicity

No adjustments will be made for multiple comparisons.

6.8. Subject Disposition

All subjects who discontinue from the study will be identified, and the extent of their participation in the study will be reported. The reason for discontinuation and the time in days to study disposition will be summarized as frequencies and percentages.

A listing of the subject disposition will also be produced.

6.9. Subject Characteristics

Baseline characteristics will be summarized for the EPP and the per-protocol population by treatment group and overall. Summaries will include descriptive statistics for continuous measures and frequencies and percentages for categorical measures.

Subject characteristics that will be summarized include:

- age (continuous and categorized into <65, 65-84 and 85+)
- gender
- race (and ethnicity)
- height
- weight
- body mass index (weight (kg) / [height (m)]²)
- country
- tobacco use at baseline
- alcohol use at baseline
- AChEI use at baseline
- memantine use at baseline
- dopaminergic therapy in levodopa equivalency dose (LED)
- time since Parkinson's disease (PD) or dementia diagnosis (whichever occurred first)
- diagnosis (PDD vs LBD)

- baseline severity of impairment as measured by CoA, Penn Parkinson's Daily Activities Questionnaire-15 (PDAQ-15), ADAS-Cog₁₃, Power of Attention (PoA), Delis-Kaplan Executive Function System (D-KEFS), Montreal Cognitive Assessment (MoCA), Neuropsychiatric Inventory (NPI), Epworth Sleepiness Scale (ESS), and Movement Disorder Society's Unified Parkinson's Disease Rating Scale (MDS-UPDRS), and
- cardiovascular risk factors (diabetes, hypertension, hyperlipidemia, coronary artery disease, cardiovascular disease, and peripheral arterial disease).

6.10. Concomitant Therapy

Prior medications are defined as those that stop before randomization (Visit 3). Concomitant medications are defined as those being taken on or after randomization (Visit 3).

A summary of concomitant medications will be presented, with frequencies and percentages for each treatment group. If the start or stop dates of therapies are missing or partially missing, to the extent that it cannot be determined whether the therapy is prior or concomitant, the therapy will be deemed concomitant.

Summary tables will also be provided for PD medications, antidepressants, and cognitive enhancing medications; specifically, a separate summary for prior and concomitant use of AChEIs will be produced.

Investigators are permitted to adjust a subject's PD, cognitive, and antipsychotic medications in order to manage motor or other symptoms during the study; the frequency and reason for change in medication will be captured in a listing.

Medications will be coded using the World Health Organization (WHO) drug dictionary.

6.11. Treatment Compliance

Compliance is defined as having taken $\geq 80\%$ to $< 120\%$ of the prescribed amount of medication. Treatment compliance information for each treatment arm will be collected through counts of dispensed and returned capsules. The number of capsules taken relative to the number expected to be taken will be summarized.

6.12. Efficacy Analyses

6.12.1. Primary Outcome and Methodology

The primary objective is to evaluate whether LY3154207, administered at 10 mg, 30 mg, and/or 75 mg QD oral dosing for 12 weeks, will show an improvement in cognition compared to placebo in subjects with mild-to-moderate LBD. This objective will be assessed in the EPP using a Bayesian MMRM analysis of the change in the CDR-CCB CoA data from baseline to Week 12. Continuity of Attention (CoA) is defined as the sum of correct responses from the Choice Reaction Time and Digit Vigilance Task with the number of Digit Vigilance Errors subtracted.

The primary analysis on CoA will occur when all subjects have had the opportunity to complete 12 weeks of treatment.

The analysis of CoA will utilize a Bayesian MMRM model. The Bayesian analysis will use uninformative priors for all terms in the model. For the model coefficients, these will be diffuse Normal distributions centered on zero. Prior for covariance matrix will follow an inverse-Wishart distribution (the multivariate generalization of an inverse gamma distribution for a variance component). The MMRM model will account for longitudinal data assessed throughout the study after 1, 2, 4, 6, 8, 10, and 12 weeks of dosing. The change in CoA from baseline to Week 12 will be the dependent variable. The model will comprise fixed (baseline value, treatment, visit, age, and use of AChEIs) with the interaction terms (treatment by visit, baseline value by visit) with repeated measures of visit within subject. Visit will be considered a categorical variable with values equal to the visit numbers at which the CoA was assessed. Covariates may be centered prior to analysis to aid model convergence.

The primary comparison will be the contrast between treatments and placebo for the Week 12 change from baseline against a null hypothesis of no difference. This will be presented as both a difference in estimated means of the 12-week change and the effect sizes over the 12 weeks. The average effect size from the last 4 visit time points (Weeks 6, 8, 10, and 12) will be the primary comparison between treatments and placebo. These will be averaged after the model has been fit.

Example codes, for the purposes of aiding programming of the primary analysis, using Bayesian MMRM and equivalent frequentist MMRM, are given below.

Bayesian MMRM Model:

```
Proc MCMC data=coa_final nbi=2000 ntu=50 nmc=10000 seed=2019143 thin=10 diag=all
plots(smooth)=all dic outpost=coa_test_final_10000
  array CoA [9] x1 - x9;
  array mu [9] mu1 - mu9;
  array covar [9, 9];
  array s [9, 9];
  array sigma [9];
  array beta_v [8] beta_v1 - beta_v8;      /* visit specific effect;
  array beta_t [3] beta_t1 - beta_t3 ;      /* treatment specific effect;
  array beta_vt [8,3] beta_vt1 - beta_vt24; /* visit treatment interaction;
  array beta_bv [8] beta_bv1 - beta_bv8;    /* baseline visit interaction;

begincnst;
  call identity(s);
endcnst;

parms beta0 beta1 beta2 beta3 0;
parms beta_v1 beta_v2 beta_v3 beta_v4 beta_v5 beta_v6 beta_v7 beta_v8 0 ;
parms beta_t1 beta_t2 beta_t3 0;
parms beta_vt1 beta_vt2 beta_vt3 beta_vt4 beta_vt5 beta_vt6 beta_vt7 beta_vt8 beta_vt9
beta_vt10 beta_vt11 beta_vt12 beta_vt13 beta_vt14 beta_vt15 beta_vt16 beta_vt17 beta_vt18
beta_vt19 beta_vt20 beta_vt21 beta_vt22 beta_vt23 beta_vt24 0;
parms beta_bv1 beta_bv2 beta_bv3 beta_bv4 beta_bv5 beta_bv6 beta_bv7 beta_bv8 0;
parms covar ;

%macro tprior1;
%do i = 1 %to 8;
  prior beta_v&i ~ N (0, prec=0.00001);
  prior beta_bv&i ~ N (0, prec=0.00001);
%end;
%do i = 1 %to 3;
  prior beta_t&i ~ N (0, prec=0.00001);
%end;
```

```

%do i = 1 %to 24;
    prior beta_vt&i ~ N (0, prec=0.00001);
%end;
%mend;
%tprior1;

prior beta0 ~ N (0, prec=0.00001);  /* overall intercept;
prior beta1 ~ N (0, prec=0.00001);  /* baseline coefficient;
prior beta2 ~ N (0, prec=0.00001);  /* age coefficient;
prior beta3 ~ N (0, prec=0.00001);  /* AChEI coefficient;
prior covar ~ iwish(9, S);

do i=1 to 9;
if trt > 1 then do;
    if i>1 then mu[i]=beta0+beta1*base+beta2*age+beta3*AChEI+beta_t[trt-1]+beta_v[i-1]+beta_vt[(i-1),(trt-1)] +beta_bv[i-1]*base ;
    else mu[i]=beta0+ beta1*base + beta2*age + beta3*AChEI+ beta_t[trt-1];
    end;
    else if trt eq 1 then do;
    if i>1 then mu[i]=beta0+ beta1*base + beta2*age + beta3*AChEI + beta_v[i-1] + beta_bv[i-1]*base;
    else mu[i]=beta0 + beta1*base + beta2*age + beta3*AChEI;
    end;
end;
do i=1 to 9;
    Sigma[i] = sqrt(covar[i,i]);
end;

model coa ~ mvn(mu, covar);
run;

```

Corresponding Frequentist MMRM Model:

```

proc mixed data=efficacy_data order=data;
class treatmentt subject visit AChEI;
model CFB_CoA = base treatment visit visit*base treatment*visit age AChEI/
ddfm=kr outp=pred solution residual;
repeated visit/subject=subject type=un ;
lsmeans trement*visit /pdiff cl alpha=0.05;
ods output lsmeans=lsmean diffs=diff;
run;

```

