All subjects in the evaluable patient population (EPP) will be considered for the efficacy analysis. The primary analysis on CoA will occur when all subjects complete 12 weeks of treatment. The analysis of CoA will utilize a Bayesian MMRM model. The Bayesian analysis may use uninformative priors for all terms in the model. These will be diffuse Normal distributions centered on zero. Priors for variance will follow an inverse gamma distribution. Further details of the Bayesian analysis will be provided in the SAP. The MMRM model will account for longitudinal data assessed throughout the study, after 1, 2, 4, 6, 8, 10, and 12 weeks of dosing. The change of CoA from the baseline to Week 12 will be the dependent variable.

The model will comprise fixed (baseline value, treatment, visit) and random effects (subject) and the interaction terms (treatment by visit, baseline value by visit). Unstructured variance structure will be applied in the model, but if it fails to converge, other suitable structures will be investigated. The primary comparison will be the contrast (difference in least squares mean) between treatments and placebo for the Week 12 change from baseline.

The secondary efficacy outcomes: the change from baseline at 12-week time point of total scores (or composite values) of Alzheimer's Disease Cooperative Study – Clinician Global Impression of Change (ADCS-CGIC), CDR-CCB Power of Attention (PoA), 13-item Alzheimer's Disease Assessment Scale – Cognitive subscale (ADAS-Cog₁₃), Montreal Cognitive Assessment (MoCA), Neuropsychiatric Inventory (NPI), Epworth Sleepiness Scale (ESS), Movement Disorder Society's Unified Parkinson's Disease Rating Scale (MDS-UPDRS), Penn Parkinson's Daily Activities Questionnaire 15 (PDAQ-15), and Delis–Kaplan Executive Function System (D-KEFS) will follow the same analysis method as above.

Missing records in some scales (e.g., ADAS-Cog) will be imputed as detailed in the statistical analysis plan. For the scales where the imputation is not done, if any item is missing, any total or sum involving that item will be considered missing. No adjustment for multiple comparisons will be made.

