10.3.3. Efficacy Analyses

10.3.3.1. Primary Analyses

The primary analysis on CoA will occur when all subjects complete 12 weeks of treatment. The analysis of CoA will utilize a Bayesian MMRM model. The Bayesian analysis may use uninformative priors for all terms in the model. These will be diffuse Normal distributions centered on zero. Priors for variance will follow an inverse gamma distribution. Further details of the Bayesian analysis will be provided in the SAP. The MMRM model will account for longitudinal data assessed throughout the study, after 1, 2, 4, 6, 8, 10, and 12 weeks of dosing. The change of CoA from the baseline to Week 12 will be the dependent variable. The model will comprise fixed (baseline value, treatment, visit) and random effects (subject) and the interaction terms (treatment by visit, baseline value by visit). Unstructured variance structure will be applied in the model, but if it fails to converge, other suitable structures will be

investigated. The primary comparison will be the contrast (difference in least squares mean) between treatments and placebo for the Week 12 change from baseline.

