5.2. Determination of Sample Size

Approximately 750 subjects will be screened to achieve 340 randomized subjects. The randomization will be 1:1:1:1 to LY3154207 (10, 30, or 75 mg QD) or placebo treatment arms.

CCI

If the true effect size for LY3154207 relative to placebo on the CoA is 0.4 with the sample size of 340, there will be greater than 80% probability of passing this criterion. A 20% discontinuation rate by Week 12 has been accounted for in the sample size determination.

Sample size estimation was based on an article by Wesnes et al. (2005) where the difference in mean change from baseline for rivastigmine compared to placebo and the pooled standard deviation (SD) for CoA were estimated as 5.7 units and 18 units, respectively. The rivastigmine effect corresponded to a reduction in the deficit of subjects compared to age-matched healthy volunteers of approximately 45%. Based on this result, the effect size of 0.4 in this study corresponds to a mean difference of 7.2 units (approximately 57% reduction in the deficit).

This sample size will allow assessment of the in-clinic blood pressure (BP) and pulse rate (PR) values on the first day of dosing in order to evaluate any changes after the first dose of treatment that was seen in Phase 1. If the SD of the in-clinic systolic blood pressure (SBP) value is assumed to be 15 mm Hg, then the difference from the mean to the upper limit of a 95% confidence interval (CI) of the change from baseline in SBP relative to placebo is expected to be <4.7 mm Hg. If there is any initial rise in BP or PR, the in-clinic 6- and 12-week assessments along with the home blood pressure monitoring (HBPM) and ambulatory blood pressure monitoring (ABPM) measures will be used to assess whether the rise accommodates. The difference from the mean to the upper limit of a 95% CI in the change in average SBP measured at each of these visits relative to placebo is expected to be <3.5 mm Hg. This assumes an SD of 10 mm Hg and a 20% discontinuation rate.

Simulations were conducted in FACTs Version 5.1.1 using a Bayesian normal dynamic linear model (NDLM).

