6.12.5. Sensitivity Analyses

A frequentist MMRM analysis of the primary analysis will be conducted.

An alternative MMRM analysis of change in CoA from baseline to Week 12, using the average change from baseline over Week 6 to Week 12 as the response variable, may also be considered. If there is a treatment difference prior to Week 12, which remains through to Week 12, this approach may be more sensitive than just looking at Week 12.

If baseline values are imputed from screening values in the primary analysis of CoA, a sensitivity analysis will be conducted to compare this approach with excluding subjects with missing baseline scores.

Differences in baseline characteristics of the treatment groups may be investigated using the Chi-squared test and 2 sample t-tests for categorical and continuous variables, respectively, if appropriate.

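### SAP 6.12.1 names two different quantities as the primary comparison, the Week 12 contrast and the Weeks 6–12 average effect size, and ranks neither; the protocol has Week 12 only

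*SAP*

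**What the plan says.** SAP 6.12.1 gives the same label to two quantities in one paragraph. First: "The primary comparison will be the contrast between treatments and placebo for the Week 12 change from baseline", tested against no difference. Then, after saying that the result will be shown as "both a difference in estimated means of the 12-week change and the effect sizes over the 12 weeks", it states: "The average effect size from the last 4 visit time points (Weeks 6, 8, 10, and 12) will be the primary comparison". It adds: "These will be averaged after the model has been fit". Nothing says which governs, or that they are co-primary.

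Protocol 10.3.3.1 has one statement: "The primary comparison will be the contrast (difference in least squares mean) between treatments and placebo for the Week 12 change from baseline". The protocol synopsis says the same, and the endpoint tables in both documents give only the CoA change to Week 12.

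SAP 6.12.5 lists among the sensitivity analyses an MMRM "using the average change from baseline over Week 6 to Week 12 as the response variable, may also be considered", and sets it against looking at Week 12 alone.

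On power, SAP 5.2 says that at a true effect size of 0.4 with 340 subjects "there will be greater than 80% probability of passing this criterion". The criterion itself is blacked out in the public copy.

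**The concern.** The primary objective is to test a hypothesis of improvement in cognition, and the plan quotes a probability of meeting a success criterion. A reader of 6.12.1 cannot say which of two numbers answers that objective for a given dose. One can cross a threshold while the other does not, and the choice is not neutral. An effect that is constant from Week 6 favours the average, which has the smaller standard error. An effect still growing at Week 12 favours the Week 12 contrast.

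Three points make it harder to settle from the text:

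- The averages in 6.12.1 and 6.12.5 are built differently. One averages effect sizes after the fit; the other uses average change as the response.
- The text does not say which SD turns a difference into an effect size. The Bayesian example code derives a visit-specific one.
- Neither code block forms the four-visit average. The Bayesian block stops at visit-level parameters and the frequentist block at visit-level LS means.

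**Working it through.** **The plan's own figures.** 0.4 × 18 = 7.2 CoA units, and 7.2 / 5.7 × 45% = 56.8%, so the stated 7.2 units and 57% reproduce. The probability above 80% can be neither confirmed nor refuted: the criterion is blacked out, and SAP 5.2 says the simulations used a Bayesian normal dynamic linear model.

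**Inputs from the documents.** 340 subjects randomized 1:1:1:1 gives 85 per arm; with 20% discontinuation, 85 × 0.8 = 68. Effect size 0.4; SD 18.

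**Assumptions, not in the documents.** 68 per arm at all four visits; equal SD at each visit; between-visit correlation either compound symmetry (CS) with r = 0.4 to 0.8 or AR(1) with 0.6 to 0.9; normal approximation; one-sided thresholds of 2.5%, 5%, 6.8% and 10%.

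**Standard errors.** Week 12: √(2/68) = 0.1715 SD units, or 3.09 CoA units. For the average, the ratio to this is √(w′Rw) with w = 1/4 for each visit; under CS it equals √((1+3r)/4).

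| Structure | SE ratio, average to Week 12 | Correlation of the two estimates |
|---|---|---|
| CS, r 0.4 to 0.8 | 0.742 to 0.922 | 0.742 to 0.922 |
| AR(1), 0.6 to 0.9 | 0.769 to 0.939 | 0.707 to 0.916 |

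**Constant effect of 0.4 at Weeks 6 to 12** (bivariate normal, per dose versus placebo):

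| One-sided threshold | Week 12 passes | Average passes | Exactly one passes |
|---|---|---|---|
| 2.5% | 0.645 | 0.700–0.882 | 0.127–0.265 |
| 5% | 0.754 | 0.800–0.933 | 0.104–0.199 |
| 6.8% | 0.800 | 0.840–0.951 | 0.091–0.168 |
| 10% | 0.853 | 0.886–0.969 | 0.073–0.128 |

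The 6.8% row is the level at which Week 12 power is 80%: 0.4/0.1715 = 2.332; 2.332 − 0.842 = 1.490; upper tail 0.068. It is a reference point, not the trial's rule. Across all rows the average passes alone in 0.053–0.251 and Week 12 passes alone in 0.006–0.036.

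**Effect still rising** (illustrations, over the same thresholds):

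- 0.1, 0.2, 0.3, 0.4 at Weeks 6, 8, 10, 12: the average estimates 0.25 (4.5 units) and Week 12 estimates 0.40 (7.2 units). Exactly one passes in 0.178–0.307; Week 12 alone in 0.139–0.305.
- Linear growth from baseline, 0.20, 0.27, 0.33, 0.40: the average estimates 0.30 (5.4 units). Exactly one passes in 0.128–0.236; Week 12 alone in 0.062–0.194.

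**Null case, only if passing on either comparison counted.** The per-dose error would be 0.034–0.042 instead of 0.025, 0.066–0.080 instead of 0.05, and 0.128–0.153 instead of 0.10. The SAP states no such rule.

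**The case against.** The strongest reply is that nearly everything else points to Week 12: the endpoint tables, the objectives, both protocol statements, and 6.12.5, which treats Week 12 as the reference. On that view one sentence is out of line, and it may only name the headline effect-size summary after the two forms of presentation are introduced. This is a fair reading and supports Week 12 as the default. But the sentence says outright that the average is the primary comparison between treatments and placebo. A reader who takes it as a refinement of the previous sentence reaches the opposite answer.

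Other points stand in part:

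- The blacked-out criterion may name the quantity tested. That would settle the intent but leave the conflicting text.
- Protocol 10.3.1 and SAP 6.2 allow analysis changes without an amendment unless a principal feature changes, with the justification in the study report. So departing from the protocol is not in itself a fault; the departure is simply not identified as one.
- The discordance figures rest on assumed correlations and thresholds. They also ignore that CoA is missing at every virtual visit during the pandemic (SAP 6.12.7). They show that the two readings differ materially; they do not predict this trial.
- The code is offered only as an example, and code that stops at visit level is compatible with averaging afterwards. It does not contradict the text, but it does not resolve it.
- The trial is exploratory, with no efficacy or futility stopping and no multiplicity control, and 6.12.1 already plans to show the Week 12 difference and the effect sizes. This limits the harm.

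**Conclusion.** The concern holds. SAP 6.12.1 contradicts itself on the primary comparison, and its averaging sentence departs from the protocol and sits badly with SAP 6.12.5. This conclusion is textual and depends on no power figure.

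On size, under the assumptions listed, the two readings give different verdicts for a dose in roughly 7–26% of trials with a constant effect and 13–31% with the two rising profiles. Which one wins depends on the time course. Error inflation is conditional on an either-passes rule that the plan does not contain.

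The consequence is that the headline result is not identified. SAP Section 3 says Version 3 was approved after unblinding and describes its edits as ALCOA-related and administrative. Nothing in the documents shows when the averaging sentence was introduced, and no inference about timing is drawn.

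**What to change.** - Name one primary comparison in 6.12.1. The default is the protocol's Week 12 contrast, each dose versus placebo, from the Bayesian MMRM.
- Depart from that default only if dated pre-unblinding records (SAP Versions 1 and 2, the interim SAP, the unredacted success criterion) show that the average was intended. If so, state it as a change from Protocol 10.3.3.1 and give the justification there and in the study report.
- Label the other quantity secondary or sensitivity. Give it one definition (averaged after the fit, or average change as the response), name the SD used for the effect size, and align 6.12.5.
- Record the edit as made after unblinding. Rewording cannot restore prespecification, so the study report should give both results for every dose with their roles.
- Minor: make the visit list match the schedule and code. The text lists seven times; the code has nine, consistent with CDR-CCB testing at Visits 3 to 11.

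The cost is small: wording, a check of dated records, and stated roles for results largely planned already. Keeping Week 12 primary gives up an SE that is about 6–26% smaller for the average under the assumptions above.
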